9.7.1 Sample Size

Table 8: Power (%) to Detect Safety Events

Event Frequency	N = 30	N = 60	N = 120
$\geq 10\%$ Very Common	96	>99	>99
$\geq 1\%$ Common	26	45	70
$\geq 0.1\%$ Uncommon	3	6	11
$\geq 0.01\%$ Rare	<1	<1	1

Table 9: Precisions of Binomial Confidence Intervals

N	95% CI
30	31-69
60	37-63
120	40-60

Table 10: Objective 1 -Minimum Detectable Difference in Proportion Responders with 80% Power (N = 50 per group)

Assumed Proportion Responders comparator arm (p_c)	Minimum detectable difference in response rate ($p_c - p_e$)
0.50	0.27
0.60	0.27
0.70	0.27
0.80	0.26
0.90	0.22

Table 11: Objective 2 - Minimum Detectable Difference in Proportion Responders with 80% Power

Assumed Proportion Responders comparator arm (p_c)	Minimum detectable decrease in response rate ($p_c - p_e$)
0.40	0.23
0.50	0.24
0.60	0.25
0.70	0.25
0.80	0.23
0.90	0.20

10.2 Protocol Deviations

Table 12: Distribution of Protocol Deviations by Category, Type and Treatment Group, All Enrolled Subjects

Category	Deviation Type	Group 1: Simultaneous Administration (N=X)		Group 2: Sequential Administration (N=X)		Group 3: HIV4 Only (N=X)		All Subjects (N=X)	
		# of Subj.	# of Dev.	# of Subj.	# of Dev.	# of Subj.	# of Dev.	# of Subj.	# of Dev.
Eligibility/enrollment	Any type								
	Did not meet inclusion criterion	x	x	x	x	x	x	x	x
	Met exclusion criterion								
	ICF not signed prior to study procedures								
	Other								
Treatment administration schedule	Any type								
	Out of window visit								
	Missed visit/visit not conducted								
	Missed treatment administration								
	Delayed treatment administration								
	Other								
Follow-up visit schedule	Any type								
	Out of window visit								
	Missed visit/visit not conducted								
	Other								
Protocol procedure/assessment	Any type								
	Incorrect version of ICF signed								
	Blood not collected								
	Too few aliquots obtained								
	Specimen result not obtained								
	Required procedure not conducted								
	Required procedure done incorrectly								

Table 12: Distribution of Protocol Deviations by Category, Type and Treatment group, All Enrolled Subjects (continued)

Category	Deviation Type	Group 1: Simultaneous Administration (N=X)		Group 2: Sequential Administration (N=X)		Group 3: HIV4 Only (N=X)		All Subjects (N=X)	
		# of Subj.	# of Dev.	# of Subj.	# of Dev.	# of Subj.	# of Dev.	# of Subj.	# of Dev.
	Study product temperature excursion								
	Specimen temperature excursion								
	Other								
Treatment administration	Any type								
	Required procedure done incorrectly								
	Study product temperature excursion								
	Other								

N = Number of subjects enrolled

12.2.2 Displays of Adverse Events

Table 13: Solicited Adverse Event Grading Scale – Local

Local (Injection Site) Reactogenicity Grading			
Local (Injection Site) Reaction	Mild (Grade 1)	Moderate (Grade 2)	Severe (Grade 3)
Pain – experienced without touching the injection site (spontaneous discomfort)	Subject is aware of pain, but it does not interfere with daily activity, and no pain medication is taken	Subject is aware of pain; there is interference with daily activity or it requires repeated use of a non-narcotic pain reliever for >24 hours	Subject is aware of pain, and it prevents daily activity or requires any use of a narcotic pain reliever
Tenderness – hurts only when injection site is touched or the arm is moved	The area immediately surrounding the injection site hurts only when touched or with arm motion, and it does not interfere with daily activity	The area immediately surrounding the injection site hurts when touched or with arm motion, and it interferes with daily activity	The area immediately surrounding the injection site hurts when touched or with arm motion, and it prevents daily activity
Pruritus (Itching)	Does not interfere with daily activity	Interferes with daily activity	Prevents daily activity
Ecchymosis (Bruising)*	Does not interfere with daily activity	Interferes with daily activity	Prevents daily activity
Erythema (Redness)*	Does not interfere with daily activity	Interferes with daily activity	Prevents daily activity
Induration (Hardness)/Swelling*	Does not interfere with daily activity	Interferes with daily activity	Prevents daily activity
Local (Injection Site) Reactogenicity Measurements			
Local (Injection Site) Reaction	Small (Grade 1)	Medium (Grade 2)	Large (Grade 3)
Ecchymosis (Bruising)*	<20 mm	20 mm – 50 mm	>50 mm
Erythema (Redness)*	<20 mm	20 mm – 50 mm	>50 mm
Induration (Hardness)/Swelling*	<20 mm	20 mm – 50 mm	>50 mm

Table 14: Solicited Adverse Event Grading Scale - Systemic

Subjective Systemic Reactogenicity Grading			
Systemic (Subjective)	Mild (Grade 1)	Moderate (Grade 2)	Severe (Grade 3)
Feverishness (Chills/Shivering/Sweating)	No interference with daily activity	Some interference with daily activity	Significant interference, prevents daily activity
Fatigue (Tiredness)	No interference with daily activity	Some interference with daily activity	Significant interference, prevents daily activity
Malaise (General Unwell Feeling)	No interference with daily activity	Some interference with daily activity	Significant interference, prevents daily activity
Myalgia (Body Aches/Muscular Pain)*	No interference with daily activity	Some interference with daily activity	Significant interference, prevents daily activity
Arthralgia (Joint Pain)*	No interference with daily activity	Some interference with daily activity	Significant interference, prevents daily activity
Headache	No interference with daily activity	Some interference with daily activity	Significant interference, prevents daily activity
Nausea	No interference with daily activity	Some interference with daily activity	Significant interference, prevents daily activity
Quantitative Systemic Reactogenicity Grading			
Systemic (Quantitative)	Mild (Grade 1)	Moderate (Grade 2)	Severe (Grade 3)
Fever# - oral [†]	38.0°C – 38.4°C 100.4°F – 101.1°F	38.5°C – 38.9°C 101.2°F – 102.0°F	>38.9°C >102.0°F
* Not at injection site.			
# Oral temperature assessed on Day 1 prior to the first study vaccination will be considered as baseline. A fever can be considered not related to the study product if an alternative etiology can be documented.			

Table 15: Vital Signs Adverse Event Grading Scale

For Individuals 19-64 years of age, pulse and blood pressure [#] will be graded as follows:			
Physiologic Parameter	Mild (Grade 1)	Moderate (Grade 2)	Severe (Grade 3)
Bradycardia - beats per minute	45 – 46	40 – 44	<40
Tachycardia - beats per minute	101 – 130	131 – 155	>155
Hypotension (systolic) mmHg	80 – 84	75 – 79	<75
Hypotension (diastolic) mmHg	50 – 54	45 – 49	<45
Hypertension (systolic) mmHg	151 – 155	156 – 160	>160
Hypertension (diastolic) mmHg	96 – 100	101 – 105	>105
[#] Pulse and blood pressure assessed on Day 1 prior to the first study vaccination will be considered as baseline.			

12.4.1 Individual Laboratory Measurements and Abnormal Laboratory Values

Table 16: Laboratory Adverse Event Grading Scale

Hematology	Mild (Grade 1)	Moderate (Grade 2)	Severe (Grade 3)
WBC 10 ³ /μL (Decrease)	2.5 – 3.9	1.5 – 2.4	<1.5
WBC 10 ³ /μL (Increase)	10.6 – 15.0	15.1 – 20.0	>20.0
Hgb g/dL (Decrease) (Female)	10.1 – 11.4	8.5 – 10	<8.5
Hgb g/dL (Decrease) (Male)	11.0 – 12.4	9.5 – 10.9	<9.5
Platelets 10 ³ /μL (Decrease)	125 – 139	100 – 124	<100
Platelets 10 ³ /μL (Increase)	416 – 550	551– 750	>750
Chemistry	Mild (Grade 1)	Moderate (Grade 2)	Severe (Grade 3)
ALT IU/L (Increase) (Female)	44 – 100	101 – 200	>200
ALT IU/L (Increase) (Male)	61 – 138	139 – 275	>275
Total Bilirubin mg/dL (Increase) – when accompanied by any increase in ALT	1.30 – 1.59	1.60 – 1.80	>1.80
Total Bilirubin mg/dL (Increase) – when ALT is normal	1.30 – 1.89	1.90 – 2.40	>2.40
Creatinine mg/dL (Increase) (Female)	1.1 – 1.7	1.8 – 2.0	>2.0
Creatinine mg/dL (Increase) (Male)	1.4 – 1.7	1.8 – 2.0	>2.0

14.1 Description of Study Subjects

14.1.1 Disposition of Subjects

Table 17: Ineligibility Summary of Screen Failures*

Inclusion/Exclusion Category	Inclusion/Exclusion Criterion	n ^a	% ^b
Inclusion and Exclusion	Number of subjects failing any eligibility criterion	x	x
Inclusion	Any inclusion criterion	x	x
	[inclusion criterion 1]	x	x
	[inclusion criterion 2]	x	x
	[inclusion criterion 3]	x	x
Exclusion	Any exclusion criterion	x	x
	[exclusion criterion 1]	x	x
	[exclusion criterion 2]	x	x
	[exclusion criterion 3]	x	x
^a More than one criterion may be marked per subject.			
^b Denominator for percentages is the total number of screen failures.			

Table 18: Analysis Populations by Treatment Group – All Enrolled Subjects*

Analysis Populations	Reason Subjects Excluded	Group 1: Simultaneous Administration (N=X)		Group 2: Sequential Administration (N=X)		Group 3: HIV4 Only (N=X)		All Subjects (N=X)	
		n	%	n	%	n	%	n	%
Safety Population	Any Reason	x	xx	x	xx	x	xx	x	xx
	Study Dose 1 Not Received								
Modified Intent to Treat	Any Reason								
	Study Dose 1 Not Received								
	No Baseline Results Available								
	No Post-Vaccination Results Available								
Per-Protocol, All Visits	Found to be Ineligible After Baseline								
Per-Protocol, Day 22	Any Reason								
	Study Dose 1 Not Received								
	No Baseline Results Available								
	No Day 22 Result Reported by Lab								
	Lost to Follow-up Before Day 22								
	Receipt of Non-Study Vaccination								
	Receipt of Immunosuppressive medication								
	Day 22 Visit Out of Window								
Per-Protocol, Day 29	Any Reason					NA	NA		
	Study Dose 1 Not Received					NA	NA		
	Study Dose 2 Not Received					NA	NA		
	Study Dose 2 Out of Window					NA	NA		
	No Baseline Results Available					NA	NA		

Table 18: Analysis Populations by Treatment Arm – All Enrolled Subjects * (continued)

	No Day 29 Result Reported by Lab					NA	NA		
	Lost to Follow-up Before Day 29					NA	NA		
	Receipt of Non-Study Vaccination					NA	NA		
	Receipt of Immunosuppressive medication					NA	NA		
	Day 29 Visit Out of Window					NA	NA		
Per-Protocol, Day 43	Any Reason					NA	NA		
	Study Dose 1 Not Received					NA	NA		
	Study Dose 2 Not Received					NA	NA		
	Study Dose 2 Out of Window					NA	NA		
	Study Dose 3 Not Received	NA	NA			NA	NA		
	Study Dose 3 Out of Window	NA	NA			NA	NA		
	No Baseline Results Available					NA	NA		
	No Day 43 Result Reported by Lab					NA	NA		
	Lost to Follow-up Before Day 43					NA	NA		
	Receipt of Non-Study Vaccination					NA	NA		
	Receipt of Immunosuppressive medication					NA	NA		
	Day 43 Visit Out of Window					NA	NA		
Per-Protocol, Day 64	Any Reason	NA	NA			NA	NA		
	Study Dose 1 Not Received	NA	NA			NA	NA		
	Study Dose 2 Not Received	NA	NA			NA	NA		
	Study Dose 2 Out of Window	NA	NA			NA	NA		
	Study Dose 3 Not Received	NA	NA			NA	NA		
	Study Dose 3 Out of Window	NA	NA			NA	NA		

Table 18: Analysis Populations by Treatment Arm – All Enrolled Subjects * (continued)

	No Baseline Results Available	NA	NA			NA	NA		
	No Day 64 Result Reported by Lab	NA	NA			NA	NA		
	Lost to Follow-up Before Day 64	NA	NA			NA	NA		
	Receipt of Non-Study Vaccination	NA	NA			NA	NA		
	Receipt of Immunosuppressive medication	NA	NA			NA	NA		
Per-Protocol, Day 181	Any Reason								
	Study Dose 1 Not Received								
	No Baseline Results Available								
	No Day 181 Result Reported by Lab								
	Lost to Follow-up Before Day 181								
	Receipt of Non-Study Vaccination								
	Receipt of Immunosuppressive medication								
Per Protocol, Day 202	Any Reason			NA	NA	NA	NA		
	Study Dose 2 Not Received			NA	NA	NA	NA		
	Study Dose 2 Out of Window								
	No Baseline Results Available			NA	NA	NA	NA		
	No Day 202 Result Reported by Lab			NA	NA	NA	NA		
	Lost to Follow-up Before Day 202			NA	NA	NA	NA		
	Receipt of Non-Study Vaccination			NA	NA	NA	NA		
	Receipt of Immunosuppressive medication			NA	NA	NA	NA		
Per Protocol, Day 223	Any Reason	NA	NA			NA	NA		
	Study Dose 3 Not Received	NA	NA			NA	NA		
	Study Dose 3 Out of Window	NA	NA			NA	NA		

Table 18: Analysis Populations by Treatment Arm – All Enrolled Subjects * (continued)

	No Baseline Results Available	NA	NA			NA	NA		
	No Day 223 Result Reported by Lab	NA	NA			NA	NA		
	Lost to Follow-up Before Day 223	NA	NA			NA	NA		
	Receipt of Non-Study Vaccination	NA	NA			NA	NA		
	Receipt of Immunosuppressive medication	NA	NA			NA	NA		
N=Number of subjects enrolled									

Table 19: Subject Disposition by Treatment Group, All Enrolled Subjects*

Subject Disposition	Group 1: Simultaneous Administration (N=X)		Group 2: Sequential Administration (N=X)		Group 3: IIV4 Only (N=X)		All Subjects (N=X)	
	n	%	n	%	n	%	n	%
Screened	x	--	x	--	x	--	x	--
Enrolled/Randomized	x	100	x	100	x	100	x	100
Received Dose 1	x	xx	x	xx	x	xx	x	xx
Received Dose 2	x	xx	x	xx	NA	NA	x	xx
Received Dose 3	NA	NA	x	xx	NA	NA	x	xx
Received All Scheduled Doses ^a	x	xx	x	xx	x	xx	x	xx
Completed Blood Draw for Primary Immunogenicity Analysis ^b	x	xx	x	xx	x	xx	x	xx
Included in Per Protocol Primary Immunogenicity Analysis ^{b c}	x	xx	x	xx	x	xx	x	xx
Completed Primary Follow-up ^{a b c}	x	xx	x	xx	x	xx	x	xx
Completed Final Study Visit	x	xx	x	xx	x	xx	x	xx

N=Number of subjects enrolled
^aRefer to Listing 2 for reasons subjects discontinued from study vaccinations or terminated early.
^bThe final blood draw for Primary Immunogenicity Analysis occurs at 21 days post final dose (Day 43 for Group 1; Day 64 for Group 2; Day 21 for Group 3).
^cRefer to Listing 5 for reasons subjects are excluded from the per protocol population.

Table 20: Dates of First Dose by Site and Treatment Group for the Safety Analysis Population

Dates of Dosing	Group 1: Simultaneous Administration (N=X)	Group 2: Sequential Administration (N=X)	Group 3: HIV4 Only (N=X)	All Subjects (N=X)
[Site 1]				
Total (Entire period of enrollment)	x	x	x	x
DDMMYYYY-DDMMYYYY	x	x	x	x
....				
[Site 2]				
Total (Entire period of enrollment)	x	x	x	x
DDMMYYYY-DDMMYYYY	x	x	x	x
....				
[Repeat for all sites]				
N= Number of subjects in the Safety population.				

Table with similar format:

Table 21: Dates of Second Dose by Site and Treatment Group for the Safety Analysis Population

Table 22: Dates of Third Dose by Site and Treatment Group for the Safety Analysis Population

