- All concomitant medications (including solicitation for receipt of any non-study influenza vaccines, including those that are experimental, what type (inactivated or live attenuated), what subtype (e.g., A/H3, A/H5, A/H9) and approximate date of vaccination will be recorded on the appropriate DCF, if known and not previously collected. Prior receipt of non-seasonal influenza vaccines are not exclusionary, except influenza A/H7 vaccines (see [Section 5.1.2](#)) will be recorded on the appropriate DCF.
- Vital signs, including oral temperature, pulse, and blood pressure, will be obtained prior to the vaccination. Subjects must not eat or drink anything hot or cold, or smoke within 10 minutes prior to taking oral temperature. Note: Vital signs are not required for subjects who are discontinued from receipt of Dose 3 and are being followed for safety.

- All AE/SAEs will be recorded on the appropriate DCF. Note: Vital signs are not required for subjects who are discontinued from receipt of Dose 3 and are being followed for safety.
- A targeted physical examination, including an assessment for signs suggestive of PIMMCs, may be performed, if indicated based on review of interim medical history, by a study clinician licensed to make medical diagnoses and listed on the Form FDA 1572 as the site principal investigator or sub-investigator.
- A urine or serum pregnancy test will be performed within 24 hours prior to the vaccination on all women of childbearing potential. Results must be negative and known prior to the vaccination.
- Pre-administration reactogenicity assessments will be performed prior to the vaccination to establish baseline.
- Approximately 10 mL of venous blood will be collected immediately prior to the vaccination for safety labs WBC, Hgb, PLT, ALT, T. Bili, Cr, and performed by the central (clinical) laboratory.
- Approximately 10 mL of venous blood will be collected immediately prior to the vaccination for serum antibody assays.
- Approximately 10 mL of venous blood will be collected immediately prior to the vaccination for future research from subjects who consent, either by signing an informed consent form that includes collection of future use samples as a condition of study participation or by indicating that they opt in to sample collection for future use if the informed consent form allows the option to choose that option.

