11.6.1 Analysis Populations

The Safety Analysis population includes all subjects who received at least one dose of study vaccine.

The modified intent-to-treat (mITT) population includes all subjects who received at least one dose of study vaccine and contributed both pre- and at least one post-study vaccination venous blood samples for immunogenicity testing (HAI or Neut antibody assays) for which valid results

were reported. For analyses using the mITT population, subjects in Group 2 who discontinue treatment after receiving the single IIV4 dose (Dose 1) but prior to receiving the first dose of the H7N9 vaccine (Dose 2) will be analyzed with group 3. All other subjects will be grouped based on randomized treatment arm.

The per protocol (PP) population includes all subjects in the mITT subset with the following exclusions:

- Data from all available visits for subjects found to be ineligible at baseline.
- Data from all visits subsequent to major protocol deviations, such as:
 - Second or third study vaccination not received,
 - Second or third study vaccination received out of window,
 - Receipt of non-study licensed live vaccine within 30 days before or after each study vaccination,
 - Receipt of non-study licensed inactivated vaccine within 14 days before or after each study vaccination,
 - Receipt of immunosuppressive therapy (e.g., corticosteroids) within 30 days before or after each study vaccination.
- Data from any visit that occurs substantially out of window.

For analyses using the PP population, subjects will be grouped based on study vaccinations received.

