6.3.3. Per Protocol Population

The per protocol (PP) population includes all subjects in the mITT subset with the following exclusions:

- Data from all available visits for subjects found to be ineligible at baseline.
- Data from all visits subsequent to major protocol deviations, such as:
 - Second or third dose not received,
 - Second or third dose received out of window,
 - Receipt of non-study licensed live vaccine within 30 days before or after each study vaccination,
 - Receipt of non-study licensed inactivated vaccine within 14 days before or after each study vaccination,
 - Receipt of immunosuppressive therapy (e.g., corticosteroids) within 30 days before or after each study vaccination.
- Data from any visit that occurs out of window by more than one day.

For analyses using the PP population, subjects will be grouped based on study vaccinations received - subjects in Group 2 who discontinue treatment after receiving the single IIV4 dose (Dose 1) but prior to receiving the first dose of the H7N9 vaccine (Dose 2) will be analyzed with Group 3.

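### The Table 18 shell conflicts with SAP 6.3.3: it ties Group 2's pre-dose Day 43 sample to Dose 3 and omits visit-window rows after Day 43

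*SAP*

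**What the plan says.** SAP 6.3.3 starts from the mITT set and removes data visit by visit. For dose deviations it removes "Data from all visits subsequent to major protocol deviations, such as" "Second or third dose not received"; the next item covers a dose given out of window. A separate bullet removes "Data from any visit that occurs out of window by more than one day". Protocol 11.6.1 has the same structure with a looser window rule: "Data from any visit that occurs substantially out of window". Neither document limits the window rule to particular visits or groups.

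Table 18 (SAP section 14.1.1) is the mock-up that counts exclusions by reason. Its Per-Protocol Day 43 block includes "Study Dose 3 Not Received" and "Study Dose 3 Out of Window", marked NA for Groups 1 and 3 and left open for Group 2. The block ends with "Day 43 Visit Out of Window", open for Groups 1 and 2. The blocks for Days 64, 181, 202 and 223 have no equivalent window row.

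Protocol 8.3.6 makes Day 43 the Dose 3 visit for Group 2 and fixes the order of events: "Approximately 10 mL of venous blood will be collected immediately prior to the vaccination for serum antibody assays". The note on Listing 5 asks that exclusion reasons agree both with the analysis-populations table and with the SAP text.

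**The concern.** A sample taken before Dose 3 cannot be made invalid by what later happens to Dose 3. Group 2's Day 43 result is the secondary endpoint 21 days after the first H7N9 dose, and its counterpart in Group 1 is Day 22. Followed literally, the shell would require Group 2 subjects, but not Group 1 subjects, to go on to receive their next dose on time before their one-dose result counts in the PP summary. That later event can depend on the dose being assessed: under Protocol 5.2.3, a Grade 3 event within 8 days of a vaccination and without another explanation is among the listed reasons for withholding the next dose.

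The missing window rows raise a separate problem. Table 19 confirms that the final primary draws are Day 43 for Group 1 and Day 64 for Group 2. A programmer working from the shell would have somewhere to record an out-of-window exclusion at the first of these visits and nowhere at the second. The models of schedule effect in SAP 8.3.2 use only the PP set and compare these two visits for the H7N9 strain. Table 18 is also marked for the Preliminary Report, whose analyses SAP 6.2.1 treats as final.

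**Working it through.** This is mainly a comparison of text with table. Taking the visits with scheduled immunogenicity blood:

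| Table 18 block | H7N9 result it carries | Position relative to the next dose | Next-dose rows | Visit-window row |
|---|---|---|---|---|
| Day 22 | Group 1, after one dose | Before Dose 2 (Protocol 8.2.3) | None | Yes |
| Day 43 | Group 1, after two doses; Group 2, after one dose | Group 2: before Dose 3 (Protocol 8.3.6) | Two, open for Group 2 only | Yes |
| Day 64 | Group 2, after two doses | No further dose | Not applicable | No |
| Day 181 | None (180 days after IIV4, all groups) | No further dose | Not applicable | No |
| Day 202 | Group 1, 180 days after second dose | No further dose | Not applicable | No |
| Day 223 | Group 2, 180 days after second dose | No further dose | Not applicable | No |

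**Dose 3 not received.** The sample precedes the deviation, so 6.3.3 keeps it and the shell excludes it. This is a direct conflict. The Day 22 block shows the rule applied correctly to the same situation.

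**Dose 3 out of window.** Dose 3 and the Day 43 draw share a visit and a window, 21 (+7) days after Dose 2. A late dose will often mean a late visit, which the visit-window rule already removes. Text and shell differ only if the blood was drawn in window and the dose was given late, or if the visit fell within the one-day allowance.

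**Size.** The plan's own figures come first. Protocol 11.4.2 allows up to 15% PP loss: 60 × (1 − 0.15) = 51, against a stated minimum of 50; 30 × 0.85 = 25.5, against 25. Both reproduce. The 15% covers missed second or third vaccinations, loss to follow-up and other excluding deviations together. The samples at risk in Group 2 therefore run from 0 up to 60 × 0.15 = 9.

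If a share *s* of Group 2 were dropped and their response rate differed from the rest by *g*, the PP proportion would shift by *s* × *g*. Neither quantity is in the documents. Assuming *s* of 5% to 15% and *g* of 20 to 30 points, the shift runs from 0.05 × 20 = 1.0 point to 0.15 × 30 = 4.5 points. With *s* = 0 it is zero.

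The effect of the missing window rows cannot be computed, because no out-of-window rate is given.

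**The case against.** The strongest reply is that Table 18 is an empty mock-up. It excludes nobody; 6.3.3 defines membership, and a programmer who follows 6.3.3 would keep the Day 43 samples. The shell also shows signs of template carry-over rather than intent. It has a Day 29 block with a row for missing laboratory results, although no immunogenicity blood is scheduled that day. Its Day 202 row for a late Dose 2 is left open for Groups 2 and 3 while the other rows there are NA. This stands as an account of how the error arose, and it makes the point an inconsistency rather than a deliberate analysis choice. It does not remove the conflict: for a Group 2 subject with valid Day 43 blood and no Dose 3, Listing 5 cannot agree with both the table and the text.

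Two stronger readings are tempting. A reader might infer that the plan applies a stricter PP filter to Group 1's primary visit and exempts Group 2's. The documents do not say so. The window rule in 6.3.3 covers every visit, and the rows simply stop after Day 43, including at Day 202, which is Group 1's own visit. A reader might also infer a sizeable selection bias driven by reactions to the first H7N9 dose. Protocol 5.2.3 lists many reasons for withholding a dose and gives no frequencies, so the dependence is possible but its extent is unknown.

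The reach is also limited. SAP 8.1 makes mITT primary, and SAP 8.2 plans no formal test of the one-dose endpoint. Group 2's Day 43 H7N9 result does not enter the regression models, which use 21 and 180 days after the second H7N9 dose.

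**Conclusion.** The shell is wrong as written and should be reconciled with 6.3.3 before programming. The clear conflict is the row for Dose 3 not received; the row for Dose 3 out of window conflicts only in the narrower cases described. If the shell were followed, the effect would fall on the descriptive PP summaries of the one-dose H7N9 endpoint (Tables 29 and 31 and the related PP figures), with 0 to at most 9 of 60 Group 2 samples lost. The upper end assumes that every planned loss is a Dose 3 failure with valid Day 43 blood, which is unlikely. The mITT primary analysis and the stated sample sizes and power are unchanged.

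The missing window rows are an omission, not an exemption. Their practical weight lies in the PP-only regression models, which draw on Day 64 and the 180-day visits.

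**What to change.** In Table 18, delete the two Study Dose 3 rows from the Per-Protocol Day 43 block. Setting them to NA for Group 2 would leave rows that are NA in every group. Keep the Dose 3 rows in the Day 64 and Day 223 blocks, where the sample does follow Dose 3. Add a visit-window row to the blocks for Days 64, 181, 202 and 223, using the one-day allowance in 6.3.3. Add one sentence to 6.3.3 stating that it governs PP membership wherever it and a shell differ, and build Listing 5 on that basis. The cost is shell edits and one sentence, with no change to data collection, sample size or planned models.
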